7.4.3 Analysis of Exploratory Endpoints

The analyses of all exploratory variables defined in Section [6.1.3](#) will be performed on the FAS. Each of these variables will be summarized by treatment. If the endpoint is measured at different visits, the variable will be summarized by treatment at each visit and at Final Visit unless stated specifically otherwise.

Comparisons between treatment groups for the following binary variables will be tested using the exact CMH method as described in Section [7.4.1.1](#)

- viral resistance to ganciclovir or valganciclovir
- biopsy-proven acute rejection (BPAR)
- clinically treated acute graft rejection

Viral resistance to ganciclovir or valganciclovir is confirmed by central laboratory. Biopsy proven acute rejection (BPAR) is captured in the CRFs. For acute antibody mediated

rejection with Banff grade ≥ 1 or for T-cell mediated rejection with grade $\geq 1a$ BPAR will be “yes”. Clinically treated acute graft rejection will be from the CRF.

The time to the first adjudicated CMV disease, including CMV syndrome and CMV tissue-invasive disease will be analyzed using the same method as described in the third sensitivity analysis in Section [7.4.1.2](#)

The following count variables may be affected by duration of follow-up which is the time of last assessment from first injection plus 1. Therefore, each of the variable will be compared between treatments using Poisson regression with treatment and randomization stratum as factors offset by follow-up time. The risk ratio, 1-sided 5% p value and the 90% confidence interval for the risk ratio will be presented.

- Number of opportunistic infections other than CMV
- Number of episodes of CMV viral load of ≥ 1000 IU/mL by central assay
- Number of episodes of adjudicated CMV-associated disease, including CMV syndrome and CMV tissue-invasive disease

Classifications of opportunistic infections other than CMV: Any TEAE with the following classifications will be considered and decided by the medical and safety officers of the study team before unblinding case by case if it is an opportunistic infection: (1) SOC: Renal and Urinary disorders and HLGT= Viral infectious disorders, Chlamydial Infections disorder, Mycobacterial infectious disorders, Fungal infectious disorders, Bacterial infectious disorders, Protozoal infectious disorders; (2) SOC: Renal and Urinary disorders and HLT= Genitourinary tract inflammation and infection NEC, Bladder infections and inflammations, Renal infections and inflammation, Urethral infections and inflammations.

Count episodes of the protocol defined CMV viremia:

An episode starts with CMV viral load ≥ 1000 IU/mL by central assay and ends with two consecutive CMV viral load < 1000 IU/mL by central assay separated by at least one week in time. An episode will not be counted if it starts outside the primary study Period.

The ordinal variables below assessed by the central laboratory will be compared between treatments using the stratum-adjusted Wilcoxon rank-sum test. This test is implemented in SAS Proc Freq using the CMH2 option for tests based on row mean scores and SCORES=MODRIDIT option for use of modified standardized rank score within strata:

- Peak CMV viral load
- Cumulative viral load

Calculation of cumulative viral load:

Using the linear trapezoidal rule to calculate the area under the viral load over time curve (AUC) divided by the length of time for each subject.

The eGFR and its change from baseline will be summarized by treatment at each visit and at final visit. The change from baseline to final visit will be compared using analysis of

covariance (ANCOVA) with treatment and randomization stratum as factors and baseline value as a covariate.

Calculation of eGFR:

$$186 \times \text{serum creatinine}^{-1.154} \times \text{age}^{-0.203} \times [1.212 \text{ if Black}] \times [0.742 \text{ if Female}] ,$$

where serum creatinine is in mg/dL and age in years. The value in either bracket is 1 if the stated condition is not met. If serum creatinine is in SI units (mmol/L) instead of the US units (mg/dL) then its value needs to be converted to the US units first by multiplying a factor of 1/88.4.

Data from KTQ and SF-12 will be listed without any analysis.

The EQ-5D is an international standardized non-disease specific (i.e., generic) instrument for describing and evaluating health status. It is a measure of health-related quality of life (QOL), capable of being expressed as a single index value and specifically designed to complement other health status measures. The questionnaire will be provided in the local language of the subject. The EQ-5D has 5 domains: Mobility, Self-Care, Usual Activities, Pain/Discomfort, and Anxiety/Depression. Each domain has 5 response levels with higher score indicating worse outcome. In addition, it has a visual analogue scale that elicits a self-rating by the respondent of his/her health on a vertical, visual analogue scale where the endpoints are labeled 'The best health you can imagine' (=100) and 'The worst health you can imagine' (=0). (see Appendix 13 of the Protocol).

The EQ-5D score for each domain, the visual analog score and the corresponding changes from baseline will be summarized by treatment at each visit and at final visit.

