1.1.4 Phase 2 (CB01-202) Results

The second clinical study of ASP0113 was a multicenter, randomized, double-blind Phase 2 clinical study designed to evaluate the efficacy, immunogenicity and safety of ASP0113 in donors and CMV-seropositive recipients undergoing 5 of 6 or 6 of 6 HLA-allele-matched allogeneic HCT for the treatment of hematologic disorders [Kharfan-Dabaja et al, 2012]. A total of 108 subjects were enrolled in the study, including 14 donor/recipient pairs, and received at least one dose of Study Drug [5 mg/mL (1 mL dose)] or placebo. Recruitment of donor/ recipient pairs was found to be impractical early in the study so that arm was discontinued; the results are not discussed here. The intent-to-treat (ITT) and per protocol (PP) populations comprise 80 and 74 transplant recipients, respectively. Recipients received injections at approximately Days -5 to -3, 21 to 42 (one injection in this window, health permitting), on Day 84, and on Day 196 relative to transplantation. Results discussed below are for the PP population.

The primary efficacy endpoint of the study was the occurrence of clinically significant CMV viremia, defined as detection of CMV viremia that resulted in the initiation of CMV-specific antiviral therapy during the first year of transplant. The clinical decision to treat at the sites was based on the most current local or central CMV assay results. CMV-specific antiviral therapy was initiated for a lower percentage of recipient subjects in the ASP0113 group (47%) than in the placebo group (61.8%), but the difference was not statistically significant ($p=0.145$, Cochran-Mantel-Haenszel test stratified by site). The PP population was modified for this analysis to exclude two subjects who received CMV-specific AVT because of false positive results from the local viral load assay.

When the occurrence of CMV viremia, as defined as ≥ 500 copies/mL by a laboratory developed test (LDT) based upon the LightCycler[®] polymerase chain reaction (PCR), was evaluated in a central laboratory, the rate was lower in the ASP0113 group (33%) than in the placebo group (62%) and was statistically significant ($p=0.008$, Cochran-Mantel-Haenszel test stratified by site). Exploratory endpoints also demonstrated a delay in time to initial viremia ($p=0.003$), number of CMV infection episodes ($p=0.017$) and duration of viremia when normalized as percentage of time on study ($p=0.042$).

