Table 3: Viral Load Endpoints after 12-Month Follow-up in the CB01-202 Study – Per Protocol Population

		ASP0113 (n=40)	Placebo (n=34)	P value
Occurrence of CMV infection (\geq 500 copies/mL)		13 (33%)	21 (62%)	0.008†
Time to initial viremia (days)	Median	> 365	109.5	0.003‡
Number of CMV infection episodes	0	27 (68%)	13 (38%)	0.017§
	1	8 (20%)	14 (41%)	
	2	4 (10%)	3 (9%)	
	3	1 (3%)	3 (9%)	
	4	0	1 (3%)	
Duration of viremia (days)	Mean	10.6 (0-68)	19.4 (0-181)	0.071§
Duration of viremia (normalized as % of time on study)	Mean	4.9 (0-63)	7.6 (0-49)	0.042§
Viral load area under the curve (copies mL*days)	Mean	66,238	127,875	0.069§
	Median	0	37,000	
	Range	0-1 x 10 ⁶	0-2 x 10 ⁶	
Peak viral load (copies/mL)	Mean	2838	8971	0.061§
	Median	0	3250	
	Range	0-29,500	0-145,000	

All results are based on LightCycler[®] PCR assay for CMV (Roche Molecular Systems) using analyte specific reagents performed at the [REDACTED].

P value was computed by: †Cochran-Mantel-Haenszel test stratified by site, ‡log rank test stratified by site or §Wilcoxon rank sum.

In a post hoc analysis, the rate of the following clinical endpoints were numerically reduced, but were not statistically significant. Acute Graft vs. Host Disease (aGVHD) (grade 3-4) occurred less frequently in the ASP0113 group (5.0%) than in the placebo group (14.7%) (p=0.2364); chronic Graft vs. Host Disease (cGVHD) (high risk) occurred less frequently in the ASP0113 group (10.0%) than in the placebo group (20.6%) (p=0.3259). In addition, the incidence rate of a composite endpoint of CMV EOD, mortality (overall), aGVHD (grade 3-4), and cGVHD (high risk) was lower in the ASP0113 group (32.5%) than in the placebo group (52.9%), although the difference was not statistically significant (p=0.1719).

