7.4.3 Analysis of Exploratory Endpoints

The exploratory endpoints in this study include:

- Number of opportunistic infections other than CMV through one year post first Study Drug injection.
- Time to first CMV viremia (defined as plasma viral load of ≥ 1000 IU/mL by central assay) through one year post first Study Drug injection.
- Time to first adjudicated CMV disease, including CMV syndrome and CMV tissue-invasive disease, through one year post first Study Drug injection.
- Number of episodes of CMV viral load of ≥ 1000 IU/mL by central assay through one year post first Study Drug injection.
- Peak CMV viral load through one year first Study Drug injection.
- Viral load area under the curve (AUC), as a measure of “cumulative viral load” through one year post first Study Drug injection.
- Number of episodes of adjudicated CMV-associated disease, including CMV syndrome and CMV tissue-invasive disease, through one year post first Study Drug injection.
- Incidence of viral resistance to ganciclovir or valganciclovir through one year post Study Drug injection as determined by a central laboratory assay.
- Incidence of biopsy-proven (T or B cell) rejection (BPAR)(Banff 2007 Grade ≥ 1) through one year post Study Drug injection.
- Estimated glomerular filtration rate (eGFR) at the last study visit calculated using the 4 variable MDRD formula.
- Incidence of clinically treated acute graft rejection rate through one year post Study Drug injection.
- Health economic and outcomes research (HEOR) scores.
- Patient-reported outcomes:
 - EQ-5D (EuroQol-5 dimensions 5 levels) will be used as a preference-based utility measure of patients’ quality of life.
 - KTQ (Kidney Transplant Questionnaire) will be used to evaluate transplant-specific patients’ quality of life.
 - SF-12v2 (Short Form Health Survey version 2) will be used to evaluate the overall patients’ quality of life.
- Healthcare resource utilization:
 - Resource use will be collected including the following: hospitalizations recorded as number of days in the Intensive Care Unit, Step-down Unit, and general medical ward, (including emergency room visits greater than 24 hours);) also non-protocol- related physician visits and emergency room visits less than 24 hours.

Number of episodes of CMV viral load of ≥ 1000 IU/mL and number of episodes of adjudicated CMV-associated disease will each be compared between treatments using Poisson regression controlling for follow-up period and stratification factors.

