6.1.3 Exploratory Efficacy Endpoints

- Number of patients with at least one opportunistic infections other than CMV
- Time to first CMV viremia (defined as plasma viral load of ≥ 1000 IU/mL by central assay) through one year post study first Study Drug injection.
- Time to first adjudicated CMV disease, including CMV syndrome and CMV tissue-invasive disease, through one year post first Study Drug injection.
- Number of episodes of CMV viral load of ≥ 1000 IU/mL by central assay through one year post first Study Drug injection.
- Peak CMV viral load through one year post first Study Drug injection.
- Viral load area under the curve (AUC) adjusted for duration through one year post first Study Drug injection.
- Number of episodes of adjudicated CMV-associated disease, including CMV syndrome and CMV tissue-invasive disease, through one year post first Study Drug injection.

- Proportion of subjects with viral resistance to ganciclovir or valganciclovir through one year post first Study Drug injection as determined by central laboratory assay.
- Proportion of subjects with biopsy-proven (T or B cell) acute rejection (BPAR) (Banff 2007 Grade \geq 1) through one year post first Study Drug injection.
- Estimated glomerular filtration rate (eGFR) at the last study visit calculated using the 4 variable MDRD formula.
- Proportion of subjects with clinically treated acute graft rejection through one year post first Study Drug injection.

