7 STATISTICAL METHODOLOGY

7.1 General Considerations

All statistical analyses and summary information will be generated according to this analysis plan and any deviations from this plan will be documented in the clinical study report. Any numerical rounding should be performed at the end of calculations. The p-values will be displayed with 3 decimal places. Statistical significance will be determined prior to rounding the p-value.

For continuous variables, descriptive statistics will include the number of subjects (n), mean, standard deviation, median, minimum and maximum. Frequencies and percentages will be displayed for categorical data. Percentages by categories will be based on the number of subjects with no missing data thus the percentages will add up to 100%. Baseline will be the last non-missing value on or prior to first study drug unless otherwise specified.

All efficacy comparisons will be tested at the 1-sided 0.05 significance level. Confidence intervals for efficacy estimates, if provided, will be constructed at 2-sided 90% level.

All data processing, summarization, and analyses will be performed using SAS® Version 9.1.3 or higher on Unix.

This SAP includes the data analysis for the primary study period (ie, 1-year post first study drug injection) which is defined as data collected through day 380 (=365+14+1 day). Certain data summary will consider analysis window as specified in each section. The long-term follow-up period is not covered by this SAP and will be managed in a separate SAP.

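### The exploratory count endpoints use plain Poisson regression with no dispersion allowance, so their p-values and intervals hold only if variance equals mean

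*SAP*

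**What the plan says.** SAP 7.4.3 groups three counts together because they may depend on length of follow-up, and compares each "using Poisson regression with treatment and randomization stratum as factors offset by follow-up time". For reporting it states: "The risk ratio, 1-sided 5% p value and the 90% confidence interval for the risk ratio will be presented". This agrees with the general rule in SAP 7.1: "All efficacy comparisons will be tested at the 1-sided 0.05 significance level".

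Protocol 7.4.3 plans the same type of model for the two CMV counts, which "will each be compared between treatments using Poisson regression controlling for follow-up period and stratification factors".

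For these counts neither document mentions a scale parameter, a negative binomial model, a robust variance or a check of dispersion. The only sandwich estimator in the SAP is in 7.4.4, for the repeated-measures model of immune responses.

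The endpoints are exploratory. SAP 6.1.3 lists, for example, "Number of episodes of CMV viral load of ≥ 1000 IU/mL by central assay through one year post first Study Drug injection". Under SAP 7.4.3 a viremia episode ends only after two consecutive central values below 1000 IU/mL at least a week apart, so one subject can contribute more than one episode.

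**The concern.** Plain Poisson regression does not estimate the spread of the counts. It takes the variance within each treatment and stratum group to equal the mean, after allowing for follow-up. If subjects differ in their underlying risk, the variance exceeds the mean, the standard errors are too small, and the p-values and intervals overstate the evidence. If counts are mostly 0 or 1, the variance falls below the mean and the error goes the other way.

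The documents contain one count distribution for a similar endpoint. Protocol Table 3, from the earlier ASP0113 trial in hematopoietic cell transplant (HCT) recipients, has a row block labelled "Number of CMV infection episodes". In both arms the variance is above the mean. The sponsor analysed those counts with a Wilcoxon rank-sum test, which does not need the Poisson assumption.

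At stake is the calibration of three exploratory comparisons.

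**Working it through.** **Inputs (Protocol Table 3).** Subjects with 0, 1, 2, 3 and 4 episodes: ASP0113 27, 8, 4, 1, 0 (n = 40); placebo 13, 14, 3, 3, 1 (n = 34).

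**Reproducing the stated figure.** The first line of that block reads "27 (68%) 13 (38%) 0.017". A two-sided Wilcoxon rank-sum test on the rebuilt counts gives p = 0.0168 without and 0.0171 with continuity correction. This matches the stated 0.017, so the counts are read correctly.

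**Mean and variance by arm.**

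- ASP0113: 19 episodes, mean 19/40 = 0.475. Sum of squares 33; variance (33 − 19²/40)/39 = 23.975/39 = 0.615. Ratio 1.29.
- Placebo: 33 episodes, mean 33/34 = 0.971. Sum of squares 69; variance (69 − 33²/34)/33 = 36.971/33 = 1.120. Ratio 1.15.

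**Pooled Pearson dispersion.** X² = 23.975/0.475 + 36.971/0.971 = 50.47 + 38.09 = 88.56 on 72 df, so φ = 88.56/72 = 1.23.

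**Strength of that evidence.** The chi-square test of φ = 1 gives p = 0.09 (by arm 0.10 and 0.25). A likelihood-ratio test of negative binomial against Poisson gives p = 0.17. The chi-square 95% interval for φ is 0.91 to 1.76, and a bootstrap gives 0.89 to 1.53. Without the one placebo subject who had four episodes, φ falls to (50.47 + 31.31)/71 = 1.15, p = 0.18.

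**Effect on the planned test.** The actual level of a nominal 1-sided 5% Wald test is 1 − Φ(1.645/√φ), and the coverage of the 90% interval is one minus twice that.

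| φ | 1-sided level | 90% CI coverage |
|---|---|---|
| 1.00 | 5.0% | 90.0% |
| 1.15 | 6.3% | 87.5% |
| 1.23 | 6.9% | 86.2% |
| 1.29 | 7.4% | 85.2% |
| 1.50 | 9.0% | 82.1% |
| 1.75 | 10.7% | 78.6% |

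At the lower interval limit, 1.645/√0.91 = 1.72 and the level is about 4.2%. The earlier data are thus compatible with a level of roughly 4% to 11%. At φ = 1.23 the true standard error is √1.23 = 1.11 times the Poisson one, so the Poisson standard error is about 10% too small.

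Simulated negative binomial counts with φ = 1.23, 64 or 70 per arm and means from 0.475 to 0.97 gave 6.5% to 7.0%. True Poisson counts gave 4.8% to 5.0%.

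**The same correction on Table 3.** Rate ratio 0.475/0.971 = 0.489; Poisson standard error of the log ratio √(1/19 + 1/33) = 0.288.

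- Plain Poisson: 90% CI 0.305 to 0.786, 1-sided p = 0.0065.
- Scaled by φ: standard error 0.288 × 1.109 = 0.319, 90% CI 0.289 to 0.828, p = 0.013.

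**The other direction.** Take the SAP's assumed 46% placebo viremia rate. Assume that a fraction q of viremic subjects have exactly two episodes and the rest one; q is an assumption, since the documents do not give it. Then variance/mean = (1 + 3q)/(1 + q) − 0.46(1 + q).

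| q | Variance/mean | 1-sided level |
|---|---|---|
| 0% | 0.54 | 1.3% |
| 20% | 0.78 | 3.1% |
| 30% | 0.86 | 3.8% |
| 50% | 0.98 | 4.8% |

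At a 25% rate the ratio passes 1 between q = 15% (1.45/1.15 − 0.25 × 1.15 = 0.97) and q = 20% (1.60/1.20 − 0.25 × 1.20 = 1.03).

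**Does an estimated variance repair both?** In simulation at 70 per arm, over cases with less and with more spread than Poisson, a robust variance held the 1-sided level at about 4.9% to 5.5%. Plain Poisson ranged from 1.3% to 7.0%.

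**The case against.** The strongest reply is that Table 3 does not show that this trial's counts will be overdispersed.

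- **Uncertainty.** The interval for φ includes 1, and the estimate leans partly on one subject.
- **Different setting.** Table 3 covers CMV-seropositive HCT recipients in a per-protocol set, at 500 copies/mL or more. This trial studies seronegative recipients of a seropositive donor's kidney, at 1000 IU/mL or more, in the full analysis set.
- **Unadjusted counts.** Table 3 has no follow-up offset and no strata. Protocol 1.1.4 reports deaths in 20.8% and 32.6% of recipients in the ASP0113 and placebo groups, so follow-up varied. The SAP's offset and stratum factors could absorb part of the 1.23.
- **Limits on recurrence.** The rule for ending an episode, with routine sampling monthly after Day 198, limits repeat episodes outside the weekly sampling during antiviral treatment. That favours counts of 0 or 1.
- **Little rests on it.** The primary and secondary endpoints use Cochran-Mantel-Haenszel tests. Time to first viremia is compared by log-rank, and peak and cumulative viral load by a stratified rank test.

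All of this stands, and it rules out a stronger reading that a reader might take from Table 3: that the counts are overdispersed, that the test really runs at 7%, and that the intervals for all three endpoints are too narrow. The 7% is conditional on one imprecise estimate from another population. Table 3 covers viremia episodes only, and the documents give no count distribution for opportunistic infections or CMV disease episodes.

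The reply does not justify fixing the dispersion at 1. A non-significant test in 74 subjects does not establish that variance equals mean, and doubt about the direction of the error is a reason to estimate the dispersion.

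**Conclusion.** The point holds as a gap in specification, not as a demonstrated inflation of error. The validity of the p-values and 90% intervals for the three counts depends on an assumption that the plan neither checks nor relaxes.

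For viremia episodes the size depends on the true dispersion. It is about 7% level and 86% coverage if φ = 1.23 carries over. It is roughly 4% to 11% across the interval from the earlier data, and about 1% to 4% if at most 30% of viremic subjects have a second episode at a 46% rate. For the other two counts no size can be given.

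The consequence is minor: the endpoints are exploratory, and the primary and secondary analyses do not use this model.

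**What to change.** Keep the Poisson model with treatment and randomization stratum as factors and the follow-up offset. For all three counts, pre-specify either a robust (sandwich) variance by subject or a Pearson scale estimated from the data and not fixed at 1. Name one of them in SAP 7.4.3 before hard lock and unblinding, so that the choice cannot depend on the results.

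Either is preferable to a negative binomial model here, because that model allows only extra spread and would not correct underdispersion.

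The cost is about one option in the SAS call, with no new data and no design change. Intervals may be slightly wider, and the variance estimate will be somewhat noisier where counts are sparse.
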